3.1. Study Type

Randomized, controlled, parallel-group clinical trial with blinded participants, care providers, and outcomes assessors. Patients were under continuous sedation, which ensured participant blinding. The investigator placing the headphones was not blinded due to the nature of the intervention.

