3.7.1. Randomization and Allocation

Participants were randomized to the music intervention group or the control group (quiet rest without headphones) using a computer-generated randomization list. The principal investigator remained unaware of allocation until consent was obtained.

Blinding included participants (sedated), bedside care providers, and laboratory personnel analyzing biomarker samples.

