3.7.2. Intervention

The process consisted of three stages:

1. Pre-intervention (baseline).
2. Intervention: 60-minute session of music intervention (intervention group) or quiet rest (control group).
3. Post-intervention (return to usual care).

Pain was verified using CPOT = 0 before beginning. BIS monitoring was applied when necessary; patients outside target sedation levels (BIS 40–60 or RASS –3 to –4) were excluded. Sessions occurred between 16:00 and 17:00 to align with nursing workflows and circadian cortisol patterns.

Baseline arterial blood samples for cortisol, prolactin, and IL-6 were taken at 15:55. Physiological parameters and sedative infusion data were recorded. Headphones were placed. The investigator remained silently at bedside during the session. Any agitation or discomfort led to termination of the session and documentation. Post-intervention arterial blood sampling was then performed, and physiological variables were recorded every 10 minutes during the entire session.

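### Blinding is claimed for care providers and outcome assessors, but the procedures support it only for the sedated participants and the laboratory personnel

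*Combined protocol and SAP*

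**What the plan says.** Section 3.1 gives the design as a "Randomized, controlled, parallel-group clinical trial with blinded participants, care providers, and outcomes assessors". It explains participant blinding by sedation ("Patients were under continuous sedation, which ensured participant blinding") and makes one exception: "The investigator placing the headphones was not blinded due to the nature of the intervention".

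Section 3.7.1 describes the comparator as the "control group (quiet rest without headphones", and then states: "Blinding included participants (sedated), bedside care providers, and laboratory personnel analyzing biomarker samples". The only outcome assessors it names are therefore the laboratory personnel.

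Section 3.7.2 has a 60-minute session in both arms, with headphones placed after the baseline sample. It adds that "The investigator remained silently at bedside during the session" and that "Any agitation or discomfort led to termination of the session and documentation". Physiological variables are recorded at 10-minute intervals throughout. The section does not say who records them or who judges agitation or discomfort.

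**The concern.** The arm can be read from the patient's head: headphones mean music and their absence means control. Section 3.7 adds that ICU clinical staff had been told about the study procedures, so they were in a position to know what the headphones meant. On that footing the statement that bedside staff were blinded cannot stand beside the description of the control condition.

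Two things are at stake:

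- **Differential care.** Staff who know the arm may handle or stimulate the patient differently, or adjust infusions differently, before the post-session sample. A blinded assay does not remove this.
- **Observer bias.** Some bedside judgements are made while the arm is visible. RASS is an observer rating. Section 3.3.1 requires a CPOT of 0 during the intervention as well as at baseline. Agitation or discomfort ends the session. These judgements affect how much of the intervention a patient receives, and may affect who enters the per-protocol sensitivity analysis in section 3.8.

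Readers who grade the trial on its design label would also credit it with safeguards that the procedures do not describe.

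**Working it through.** No figure in the plan depends on blinding, and the sample size in section 3.3.1 is unaffected, so there is nothing to recompute. The check sets the claim for each party beside the procedure that would have to deliver it.

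| Party | Claimed blinded? | What the procedures describe | Supported? |
|---|---|---|---|
| Participants | Yes (3.1, 3.7.1) | Continuous sedation | Yes, as described |
| Laboratory personnel | Yes (3.7.1) | Biomarker samples analysed by blinded staff | Yes, as described |
| Investigator placing headphones | No (3.1) | Stated as unblinded | Disclosed |
| Bedside care providers | Yes (3.1, 3.7.1) | Headphones in one arm only; no sham or screen | No |
| Recorder of physiology, RASS and CPOT; judge of agitation | Covered by the unqualified claim in 3.1; not named in 3.7.1 | Person not named; no separate blinded recorder | No |

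**Step 1: is the arm visible?** Music patients wear the headphones of section 3.5.2 for a piece of 30 minutes played twice (3.5.1), so 2 × 30 = 60 minutes. Controls wear none (3.7.1). Nothing described hides this difference.

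**Step 2: which outcomes have a blinded assessor?** Cortisol (primary), prolactin and IL-6 do, at the assay. For the physiological list in section 3.6, no blinded assessor is described.

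**Step 3: how far could an observer's knowledge alter the recorded value?** Section 3.6 lists six physiological measures:

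- Systolic and diastolic pressure come from an arterial catheter, heart rate from continuous ECG and respiratory rate from the ventilator. I take SpO₂ to be a monitor reading too, although its source is not spelled out. These five leave little room for judgement.
- Sedation is by BIS, an instrument reading, or by RASS, an observer score. Only RASS is open to judgement.
- Outside that list, CPOT and the decision to end a session for agitation or discomfort are also judgements.

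**Step 4: which outcomes could differential care reach?** All of them, because the care is given before the post-session sample and during the 10-minute recordings. The documents contain no data on whether care differed, so the possible bias has no derivable size.

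**The case against.** The strongest reply is that the blinding that matters most is intact. The primary and key secondary outcomes are assays run by blinded personnel, the patients are sedated, most bedside values are instrument readings, and the plan openly says that the person placing the headphones knew the arm. The plan also records sedative, analgesic and neuromuscular-blocker doses and rates (3.6). Nothing in it suggests that care actually differed.

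All of that stands, and it limits the point. It does not rescue the statement about care providers, because no described procedure could have kept the arm from them.

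A reader might infer more than the documents support:

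- **That only the assays were blinded.** Participant blinding by sedation is stated and is not in dispute here.
- **That the unblinded investigator recorded the physiology and judged agitation.** This is plausible but not stated. Nor is it stated that the investigator at the bedside was the one who placed the headphones. The point does not need either inference, since anyone present could see the arm.
- **That all six physiological measures are equally open to observer bias.** Their measurement sources say otherwise.
- **That the cortisol result is biased.** A route exists through differential care, but there is no evidence that it operated.
- **That controls should have worn silent headphones.** The headphones cancel noise (3.5.2), so silent ones could themselves change the control condition and hence the comparison. Data collection in any case ended on 28 June 2025 (3.4).

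**Conclusion.** The concern holds in this form: sections 3.1 and 3.7.1 state blinding that the trial's own procedures do not support. It is supported for two parties, the sedated participants and the laboratory personnel. It is unsupported for bedside care providers and for whoever made the bedside recordings and judgements.

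The consequence for the three biomarkers is limited to possible differential care. For RASS, CPOT and session termination, observer bias is possible as well. The magnitude of either cannot be derived.

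The conclusion assumes that no concealment measure was used beyond those described. If a screen or a separate blinded recorder was in place, the plan should say so, and the conclusion would change for the parties concerned. As written, the blinding statement is wrong and should be corrected before it is carried into any report.

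**What to change.** 1. Restate sections 3.1 and 3.7.1 along these lines: *participants (sedated) and laboratory personnel blinded; bedside care providers, the bedside investigator and bedside outcome recording not blinded.*
2. State who recorded the 10-minute values, who scored RASS and CPOT, who judged agitation or discomfort, and whether each knew the arm.
3. Report by arm the sedative and analgesic infusion data already recorded around the session, and the number of sessions ended early with reasons, as a check on differential care. Section 3.7.2 is clear only that infusion data were taken at the start. If nothing was recorded later, the infusion comparison shows starting balance only, and the report should say so.
4. If time-stamped monitor or ventilator records exist, use them for the 10-minute values. The documents do not show that they do, so this step is conditional.

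The cost is a wording change, a short table and a less favourable blinding statement. The primary analysis is unchanged and no new patient data are needed.

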3.2. Study Setting

The study was conducted in the General (Polivalent) Intensive Care Unit (ICU) of the Hospital Universitario Central de Asturias (HUCA), a major tertiary public hospital in Oviedo, Spain. HUCA is a modern, highly specialized center with advanced technological infrastructure, extensive ICU capacity, and multidisciplinary teams experienced in managing severe, complex critical illness. The polivalent ICU includes 44 beds distributed across general critical care and neuro-trauma units and provides comprehensive monitoring and life support for patients with multiorgan failure, high-risk postoperative complications, severe trauma, and complex infectious and medical conditions.

3.3. Population and Sample

3.3.1. Study Subjects

Inclusion Criteria:

- Adults aged 18 years or older.
- Admission to HUCA's polivalent ICU for at least 24 hours.
- Intubated and receiving invasive mechanical ventilation.
- Presence of an arterial catheter and/or central venous catheter.
- Sedation level between BIS 40–60 or an equivalent level on the RASS scale (–3 to –4).
- Absence of pain at baseline and during the intervention, defined as a CPOT score of 0.
- No prior exposure to music therapy or similar interventions during the current hospital stay.
- Informed consent obtained from the patient's legally authorized representative within 72 hours of presentation.

Exclusion Criteria:

- Severe neurological disease or injury incompatible with study participation.
- Severe psychiatric illness such as psychosis or schizophrenia.
- Suspected or confirmed drug or alcohol intoxication, overdose, withdrawal, or abstinence.
- Hearing impairment that limits perception of the auditory intervention.
- Cranial injuries preventing safe placement of headphones.
- Limitation of therapeutic effort, expected death within 24 hours, or confirmed brain death.
- Current treatment with systemic corticosteroids.
- Requirement for vasoactive drugs above 0.1 mcg/kg/min.
- Refusal by the responsible attending physician.

Sample Size:

Using a pilot sample of 40 patients, a between-group difference of 1.32 units in serum cortisol and standard deviations of 2.86 (control) and 1.59 (intervention) were assumed. With 80% power and $\alpha = 0.05$, 50 subjects per group were required. After adjusting for a potential 20% loss rate, the final sample size required was 63 patients per group (126 total).

3.4. Study Timeline

Data collection occurred from 1 October 2023 to 28 June 2025.

3.5. Instruments

A study-specific case report form (CRF) was created to collect all relevant variables.

3.5.1. Musical Piece

A licensed music therapist composed a 30-minute audio piece intended to promote mental and physical relaxation in sedated ICU patients. The piece was reproduced twice consecutively, for a total session duration of 60 minutes. It was characterized by a soft musical dynamic (“piano”), slow tempo, two coordinated melodic lines

(piano, synthesizer, ocean drum, acoustic guitar, soft vocals), and background nature sounds such as ocean waves, birds, fire crackling, and rain. The composition was based on a stable harmonic structure in C major, with predictable modulations to A minor, F, G, and occasional D minor. A diatonic scale was used to reinforce calmness and reduce cognitive load.

3.5.2. Headphones

The auditory intervention used Sony WH-1000XM4 noise-cancelling headphones with 40-mm diaphragms, extended frequency response (~40 kHz), integrated digital-to-analog converter with amplifier, and real-time processing to cancel ambient noise using external microphones and phase-inversion. This provided stable and high-quality sound despite the ICU environment.

3.6. Variables

Physiological variables were recorded every 10 minutes during the intervention.

Demographic and Clinical Variables:

- Age, sex, primary diagnosis at ICU admission.
- APACHE II severity score.
- Days on invasive mechanical ventilation at the time of intervention.
- Ventilatory mode and parameters, including FiO₂.
- Sedatives, analgesics, and neuromuscular blockers, with dose and infusion rate.

Physiological Parameters:

- Systolic and diastolic arterial blood pressure measured via arterial catheter.
- Heart rate via continuous ECG monitoring.
- Respiratory rate from the ventilator.
- Oxygen saturation (SpO₂).
- Level of sedation measured by BIS or RASS.

Biomarkers:

- Serum cortisol (primary biomarker), measured immediately before and after the intervention via arterial line.

- Serum prolactin and interleukin-6 (IL-6), measured at the same time points.

3.7. Procedures

Approvals were obtained from the Ethics Committee of the Principality of Asturias and HUCA administration. ICU clinical staff were informed about study procedures. Patient screening involved review of clinical records and bedside nurse consultation. Legally authorized representatives received written and verbal explanation, and informed consent was obtained prior to enrollment.

A coded identification number was assigned to each participant for confidentiality.

3.7.1. Randomization and Allocation

Participants were randomized to the music intervention group or the control group (quiet rest without headphones) using a computer-generated randomization list. The principal investigator remained unaware of allocation until consent was obtained.

Blinding included participants (sedated), bedside care providers, and laboratory personnel analyzing biomarker samples.

3.7.2. Intervention

The process consisted of three stages:

1. Pre-intervention (baseline).
2. Intervention: 60-minute session of music intervention (intervention group) or quiet rest (control group).
3. Post-intervention (return to usual care).

Pain was verified using CPOT = 0 before beginning. BIS monitoring was applied when necessary; patients outside target sedation levels (BIS 40–60 or RASS –3 to –4) were excluded. Sessions occurred between 16:00 and 17:00 to align with nursing workflows and circadian cortisol patterns.

Baseline arterial blood samples for cortisol, prolactin, and IL-6 were taken at 15:55. Physiological parameters and sedative infusion data were recorded. Headphones were placed. The investigator remained silently at bedside during the session. Any agitation or discomfort led to termination of the session and documentation. Post-intervention arterial blood sampling was then performed, and physiological variables were recorded every 10 minutes during the entire session.

3.8. Statistical Analysis

Analyses followed an intention-to-treat approach, with per-protocol sensitivity analyses. Continuous variables were summarized using mean \pm SD or median [IQR]; categorical variables using frequency and percentage.

Baseline differences were analyzed using Student's t-test or Mann–Whitney U test for continuous variables and chi-square or Fisher's exact test for categorical variables.

Primary analysis focused on the change in serum cortisol using linear mixed-effects models with fixed effects for group, time, and group \times time interaction, and random intercepts for subjects. Prolactin and IL-6 were analyzed similarly as key secondary outcomes. Non-parametric tests, including the Friedman test and Dunn post-hoc tests, were applied where model assumptions were violated.

Physiological trajectories were analyzed using repeated-measures mixed models incorporating the 10-minute time intervals.

Correlations were assessed using Pearson or Spearman coefficients. Multiple comparisons for secondary outcomes were controlled using the false discovery rate when necessary.

The significance threshold was 0.05. Analyses were performed using R version 4.4.3.

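### With one pre and one post sample, the primary cortisol model compares mean change; adjusting for baseline would be more precise, by an amount the documents do not fix.

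*Combined protocol and SAP*

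**What the plan says.** Section 3.8 sets the primary analysis: "Primary analysis focused on the change in serum cortisol using linear mixed-effects models with fixed effects for group, time, and group" by time, and "random intercepts for subjects". Prolactin and IL-6 are to be handled in the same way as key secondary outcomes.

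Section 3.6 gives cortisol two time points: "Serum cortisol (primary biomarker), measured immediately before and after the intervention via arterial line". Section 3.7.2 fixes the first: "Baseline arterial blood samples for cortisol, prolactin, and IL-6 were taken at 15:55". Section 3.7.1 confirms the randomised comparison: "Participants were randomized to the music intervention group or the control group".

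The only stated use of baseline values, apart from their place as the first time point in the model, is a significance test: "Baseline differences were analyzed using Student's t-test or Mann–Whitney U test for continuous variables". No baseline covariate and no common baseline mean is specified. The sample size in section 3.3.1 rests on "a between-group difference of 1.32 units in serum cortisol" and SDs of 2.86 (control) and 1.59 (intervention). It does not say whether these are SDs of change or of single values, and it gives no pre-post correlation.

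**The concern.** The group main effect gives each arm its own baseline mean. Randomisation makes the true baseline difference zero in expectation, so the model spends information on estimating a quantity already known. The group-by-time term then subtracts the whole observed baseline difference, as if the slope of post on baseline were 1. If the slope is below 1, chance imbalance is over-corrected; if it is above 1, it is under-corrected.

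At stake are the width of the primary confidence interval and how far a chance baseline difference at 50 to 63 per arm moves the estimate. The same applies to prolactin and IL-6.

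**Working it through.** **Inputs.** Difference 1.32; SDs 2.86 and 1.59; alpha 0.05; power 80%; loss 20% (all section 3.3.1). Two samples per patient (sections 3.6 and 3.7.2). The correlation rho and the ratio k = SD(post)/SD(pre) are not in the documents and are varied as assumptions.

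**1. The plan's own figure.** Root-mean-square SD = √((2.86² + 1.59²)/2) = 2.314. The two-sided normal approximation gives n = 2 × (2.314 × (1.960 + 0.842)/1.32)² = 48.2, so 49 per arm. The noncentral t gives 50 (power 80.6% pooled, 80.4% Welch). Then 50/0.8 = 62.5, rounded up to 63. The stated figures reproduce.

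**2. Equivalence to a change score.** In simulated complete data with 50 per arm, one data set per rho:

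| rho | Group-by-time estimate (SE), planned model | Difference in mean change (SE) | ANCOVA SE |
|---|---|---|---|
| 0.5 | −0.8521 (0.5830) | −0.8521 (0.5830) | 0.473 |
| 0.8 | −0.7846 (0.3454) | −0.7846 (0.3454) | 0.326 |

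With 20% of post values missing, the two differ slightly (for example −1.337 against −1.289), because the mixed model also uses unpaired baselines.

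**3. Variance ratio.** In units of the baseline variance, the change score has variance 1 + k² − 2·rho·k and ANCOVA has k²(1 − rho²). The first minus the second is (1 − rho·k)². ANCOVA is therefore more precise unless the slope rho·k equals 1. The ratio of ANCOVA to change score is k²(1 − rho²)/(1 + k² − 2·rho·k), which is (1 + rho)/2 when k = 1.

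| k | rho 0.5 | rho 0.7 | rho 0.9 |
|---|---|---|---|
| 0.85 | 0.62 | 0.69 | 0.71 |
| 1 | 0.75 | 0.85 | 0.95 |
| 1.1 | 0.82 | 0.92 | 1.00 |

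Simulation at k = 1 (4,000 trials per rho) gave 0.77, 0.90 and 0.96 at rho 0.5, 0.8 and 0.9, against 0.75, 0.90 and 0.95 in theory.

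**4. Power at 50 per arm (Welch, noncentral t, k = 1).**
- If 2.86 and 1.59 are SDs of change: 80.4% as planned; 90.2%, 86.3% and 82.4% with adjustment at rho 0.5, 0.7 and 0.9.
- If they are SDs of single values, the change variance is 2(1 − rho) times, and the ANCOVA variance (1 − rho²) times, the single-value variance. Change score against ANCOVA: 66% and 84% at rho 0.3; 80% and 90% at 0.5; 95% and 98% at 0.7.

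These figures use one rho and k = 1 for both arms. Randomised arms share a baseline SD in expectation, so with planning SDs as unequal as 2.86 and 1.59 this can only be approximate.

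**5. Chance imbalance.** The SE of the baseline difference is √(2/50) = 0.20 SD at 50 per arm and √(2/63) = 0.18 SD at 63. A difference beyond 0.2 SD in either direction has probability about 32% and 26%. On the single-value reading with k = 1, such a difference shifts the change-score estimate by 0.2 × 2.314 × (1 − rho): 0.23 units at rho 0.5 and 0.05 at rho 0.9, against a planned effect of 1.32.

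**6. Check on one possible remedy.** Simply dropping the group main effect while keeping only a random intercept forces equal pre and post variances. Simulated under the null at 50 per arm with k = 1.3, type I error was about 8%, while the planned change contrast stayed near 5%.

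**The case against.** The planned test is valid. It is unbiased over randomisation, holds its error rate, and its sample size reproduces. A reader might infer that the primary analysis is biased or the trial underpowered; the documents do not support that. The shortfall on the single-value reading needs rho below 0.5, and neither that reading nor that rho is stated.

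A reader might also take the rise from 80% to 90% as the expected gain. It belongs to rho = 0.5 and equal SDs. The samples bracket a 60-minute session in the same patient, so rho may be high; at rho 0.9 with equal SDs the SE falls only by a factor √0.95 = 0.975. With k = 1.1 and rho 0.9 the gain vanishes. Nor does a correlation below 1 by itself mean over-correction: at rho 0.9 and k = 1.3 the slope is 1.17 and the change score under-corrects.

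It would also be tempting to define the estimate at 17:00, or to take 15:55 as the baseline for the physiological models. Section 3.7.2 gives no clock time for the post-session sample, allows sessions to end early, and attaches 15:55 to the blood samples only. Nothing shows that the physiological models lack a baseline term.

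Finally, section 3.4 says that data collection ended on 28 June 2025, and section 3.8 is written in the past tense. A new primary model could be a change made after seeing data.

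All of this stands. It limits the size of the point and shapes the remedy. It does not alter the fact that the plan makes less than full use of the baseline sample.

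**Conclusion.** The point holds as one of efficiency and robustness, not validity. For complete pairs the planned model is a comparison of mean change. Adjusting for baseline is at least as precise apart from the negligible cost of estimating one slope, and it is strictly more precise unless the slope of post on baseline is 1. With equal pre and post SDs the variance falls by 25%, 15% or 5% at rho 0.5, 0.7 or 0.9; with unequal SDs the gain can be larger or close to nil. The algebra is certain. The size is not, because it rests on a correlation and on separate pre and post SDs that the documents do not give.

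**What to change.** Estimate the between-arm difference in post-session cortisol by ANCOVA, with baseline cortisol as covariate, and report it with a 95% CI. Use a heteroscedasticity-robust or arm-specific variance, since the assumed SDs differ. Alternatively, fit a constrained-baseline model (time and group by time, no group main effect) with unstructured, arm-specific covariance; a random intercept alone is not enough. Do the same for prolactin and IL-6, on the log scale if skewed. State what 2.86 and 1.59 are SDs of, and give the pre-post correlation from the pilot.

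This needs no new data, only a revised SAP paragraph and a changed model. If outcomes have already been analysed by arm, keep the planned analysis in the report, set the adjusted one beside it, and say when it was added.

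### The sample size expects SDs of 2.86 and 1.59 in the two arms, but the primary cortisol model as written has one residual variance; if those SDs describe change, its between-arm test is exact only when evaluable arms are equal

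*Combined protocol and SAP*

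**What the plan says.** The Sample Size paragraph of section 3.3.1 takes its inputs from a pilot ("Using a pilot sample of 40 patients"). It uses "a between-group difference of 1.32 units in serum cortisol", and "standard deviations of 2.86 (control) and 1.59 (intervention) were assumed". From these, "50 subjects per group were required". The paragraph continues "After adjusting for a potential 20% loss rate" and arrives at 63 per arm, 126 in total. It does not say whether the SDs are of cortisol levels or of the change across the session, how the pilot patients were split by arm, or how the losses are expected to divide.

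Section 3.8 makes the change in cortisol the primary analysis. The linear mixed model has effects of arm, time and their interaction, "and random intercepts for subjects". Prolactin and IL-6 follow the same approach. If model assumptions fail, the section turns to non-parametric tests, naming Friedman and Dunn, with no criterion for when to switch. It does not state in words that the residual variance is common to both arms; that is simply what the model as described implies.

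**The concern.** A random-intercept model with no variance function estimates one residual variance across both arms and both time points. With cortisol measured twice and no missing values, its interaction test is the pooled-variance t-test on change. That test relies on equal variances unless the arms are equal in size. The plan's own figures put the control variance at about three times the intervention variance.

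Two things are at stake. If the evaluable arms end up unequal, the model's standard error for the between-arm difference is too small when control is the smaller arm and too large when music is. Separately, any interval for the change within one arm would borrow the averaged variance, and so be too narrow in control and too wide in music, whatever the arm sizes.

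**Working it through.** **Inputs.** Difference 1.32, SDs 2.86 and 1.59, 80% power, 50 evaluable per arm, 20% loss, 63 per arm (section 3.3.1); alpha 0.05 (sections 3.3.1 and 3.8), taken as two-sided because that reproduces the stated size (one-sided gives 38).

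**Reproducing the sample size.** 2.86² + 1.59² = 8.180 + 2.528 = 10.708. Normal approximation: n = (1.960 + 0.842)² × 10.708 / 1.32² = 48.2 per arm. With the t distribution, power first passes 80% at 50 per arm: 80.6% pooled, 80.4% Welch. Inflation: 50 / 0.80 = 62.5, so 63. The plan's figures are correct.

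The root-mean-square SD is √(10.708 / 2) = 2.314, and this single common SD also gives 50. Both SDs do enter the calculation: by the normal approximation, 2.86 alone gives about 74 per arm and 1.59 alone about 23.

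**Size of the gap.** (2.86 / 1.59)² = 3.24. If the pilot was split 20/20 (an assumption), the 95% confidence interval for this ratio is about 1.3 to 8.2.

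**Between-arm test.** Assume 2.86 and 1.59 are SDs of change, and take equal mean change as the null. For evaluable numbers n_C and n_M:

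- model variance = [((n_C − 1) × 8.180 + (n_M − 1) × 2.528) / (n_C + n_M − 2)] × (1/n_C + 1/n_M)
- true variance = 8.180/n_C + 2.528/n_M
- r = √(model / true), and the type I error is approximately 2 × [1 − Φ(1.96 r)]

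Example, 50 control and 63 music: model SE 0.4245, true SE 0.4514, r = 0.940, type I error about 6.5%. The table adds simulated results: the pooled t-test on change (400,000 trials per row) and, where run, REML fits of the random-intercept model keeping patients with a baseline value only (16,000 fits per row).

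| Control / music | r | Formula | Pooled t | REML model |
|---|---|---|---|---|
| 63 / 63 | 1.000 | 5.0% | 5.0% | 4.9% |
| 50 / 50 | 1.000 | 5.0% | 5.1% | – |
| 45 / 55 | 0.948 | 6.3% | 6.4% | – |
| 55 / 45 | 1.055 | 3.9% | 4.0% | – |
| 50 / 63 | 0.940 | 6.5% | 6.5% | 6.6% |
| 63 / 50 | 1.063 | 3.7% | 3.8% | 3.8% |
| 44 / 57 | 0.934 | 6.7% | 6.8% | – |
| 38 / 63 | 0.876 | 8.6% | 8.7% | 8.2% |
| 63 / 38 | 1.142 | 2.5% | 2.6% | 3.0% |

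The separate-variance (Welch) test gave 5.0% to 5.1% in every row.

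**If the SDs are of levels.** With the gap placed only in the between-patient intercepts and a common residual SD (assumed to be 1), the interaction test stayed at 4.3% to 5.3% in all patterns tried (3,000 fits each).

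**Within-arm intervals, 50 per arm.** Again with SDs of change, the model SE is 2.314/√50 = 0.327. The true SEs are 2.86/√50 = 0.404 (control) and 1.59/√50 = 0.225 (music). Nominal 95% coverage is 2Φ(1.96 × 2.314/2.86) − 1 = 88.7% in control and 2Φ(1.96 × 2.314/1.59) − 1 = 99.6% in music.

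**The case against.** The best defence is that, under the trial as planned, the main result is unharmed. Allocation is 63 to 63 with 50 evaluable in each arm, and with equal arms the pooled test holds 5%. Large drift needs lopsided losses that the documents do not suggest. If 25 of 126 patients were lost at random, 19 or more would fall in control (44/57) with probability about 0.3%, and 38/63 puts every loss in control. Follow-up is about an hour, and only the music arm wears headphones; if that caused extra losses, the test would become conservative. Section 3.8 specifies no within-arm interval as a result. The null is also narrow: if music affects nobody, the randomised arms share one distribution of change, the variances are equal and the test is valid. All of this stands and limits the size of the point.

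It does not remove it. Equal evaluable arms are not assured: the loss rate is not split by arm, per-protocol sets may differ in size, and section 3.7.1 mentions no blocking. If the randomisation list were unrestricted (an assumption, given the target of 63 each), a split of 57/69 or wider would arise in about one trial in three; 57 control/69 music gives about 6.3%, and the reverse about 4.0%. Nor does the fallback rescue the plan. It has no trigger, and neither named test compares change between arms while allowing unequal variances.

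A reader might also infer that the sample size proves the plan relied on separate variances, so that the analysis contradicts it outright. It does not: a common SD of 2.314 gives the same 50 per arm.

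**Conclusion.** The mismatch is real and modest. The plan anticipates clearly different spread in the two arms and then names a model with one residual variance and no correction. If the SDs describe change, and under a null of equal mean change with unequal spread, the type I error is 5% with equal evaluable arms and about 4% to 6.5% under moderate imbalance. It reaches 8% to 9% only if nearly all losses are in control. Any model-based within-arm interval would be miscalibrated even with equal arms (about 89% and 99.6%).

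It would be tempting to conclude that the primary test is invalid or generally inflated. The documents do not support that: the planned arms are equal, the drift can go in either direction, and section 3.3.1 leaves open whether the SDs are of levels or of change. If the gap is only between patients' levels, the interaction test stays near 5%. The SDs also come from a small pilot, so the true gap could be smaller or larger. The point justifies a correction to the analysis specification. It does not put the sample size in doubt.

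**What to change.** - In section 3.8, let the residual variance differ by arm in the primary model (for example nlme with varIdent by group), or use robust standard errors, or a Welch comparison of change, with Satterthwaite-type degrees of freedom.
- Apply the same specification to prolactin and IL-6.
- In section 3.3.1, state whether 2.86 and 1.59 are SDs of levels or of change.

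The cost is one model option and two sentences. At 50 per arm the degrees of freedom fall from 98 to about 77, and power from 80.6% to 80.4%; 50 evaluable and 63 randomised per arm both stand. Section 3.4 shows that data collection has ended, but the change affects only the analysis. If the primary model has already been fitted, report both versions and say which came first.
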